#### B. Acute Effectiveness (Secondary effectiveness endpoint)

The acute success of each arm shall be determined by:

1. A subject in the FIRM-guided ablation arm shall be classified as an acute success upon elimination of all identified atrial fibrillation rotors.
2. A subject in the conventional ablation arm shall be classified as an acute success upon isolation of all pulmonary veins.

The proportion of successes in each arm will be calculated as follows:

$$\frac{n}{N}$$

Where:

$n$  = the total count of “successful” subjects in the arm in question

$N$  = the total count of subjects for that arm in the ITT group

The statistical hypothesis for this endpoint is operationalized as follows:

$H_0: p_F = p_C$

$H_A: p_F \neq p_C$

$\alpha = .05$  (two-tailed)

Where:

$p_F$  = the proportion of “successes” in the FIRM-guided ablation arm

$p_C$  = the proportion of “successes” in the conventional ablation control arm

The analysis to be performed for this endpoint will be a Chi-square test of Independence.

#### C. Long-Term Secondary Safety (safety endpoint)

Long-term safety is defined as freedom from serious adverse events related to the procedure (including those related to repeat procedures) within one year of the index procedure.

---

 Dukkipati, Srinivas R. MD, et. al. (2015). Pulmonary Vein Isolation Using the Visually Guided Laser Balloon. Journal of the American College of Cardiology. 66(12):1350-1360.

The statistical hypothesis for this endpoint is operationalized as follows:

$H_0: p_F = p_C$

$H_A: p_F \neq p_C$

$\alpha = .05$  (two-tailed)

Where:

$P_F$  = the proportion of subjects free from serious adverse events related to the procedure (including those related to repeat procedures) within one year of the index procedure in the FIRM-guided ablation arm

$p_C$  = the proportion of subjects free from serious adverse events related to the procedure (including those related to repeat procedures) within one year of the index procedure in the conventional ablation control arm

The proportion of successes in each treatment arm shall be estimated using Kaplan-Meier survival estimation.

#### D. Acute Safety (Secondary safety endpoint)

The acute safety success of either treatment arm is defined as freedom from serious adverse events related to the procedure within seven (7) days of the index procedure.

The proportion of successes in each arm will be calculated as follows:

$$\frac{n}{N}$$

Where:

$n$  = the total count of subjects presenting freedom from serious adverse events related to the procedure within seven (7) days of the index procedure.

$N$  = the total count of subjects in that arm in the ITT group

The statistical hypothesis for this endpoint is operationalized as follows:

$H_0: p_F = p_C$

$H_A: p_F \neq p_C$

$\alpha = .05$  (two-tailed)

Where:

$P_F$  = the proportion of "successes" in the FIRM-guided ablation arm

$p_C$  = the proportion of "successes" in the conventional ablation control arm

The analysis to be performed for this endpoint will be a Chi-square test of Independence.

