#### A. ***Inclusion Criteria***

Subjects are required to meet the following inclusion criteria:

1. Male or female 18 – 80 years of age.
2. Experiencing at least two (2) documented episodes of **paroxysmal** atrial fibrillation in the last 3 months preceding study entry with clinical indication for AF ablation per guidelines. At least one episode should be documented by rhythm strip or ECG.
3. Indicated for AF ablation according to current EHRA guidelines.
4. Prescribed with oral anticoagulation therapy, in indicated patients per the latest EHRA guidelines.
5. Willingness and able to remain on anti-coagulation therapy as per the latest EHRA guidelines.
6. Left atrial diameter < 5.5 cm as measured and image ((CT/TEE/TTE/ MRI or ICE) documented within previous six months up to pre-procedure.
7. Sustained AF (>5 min uninterrupted) during the electrophysiology procedure. If the subject is not experiencing spontaneous, sustained AF, it may be induced by burst pacing (typically from the coronary sinus) with or without isoproterenol infusion in conventional clinical fashion.
8. Willingness, ability and commitment to participate in baseline and follow-up evaluations.
9. Signed patient informed consent form.

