#### 7.4 RANDOMIZATION AND SUBJECT IDENTIFICATION

Randomization will occur if the subject is deemed eligible following screening baseline assessments and has signed the study informed consent form. Subject identification number will be assigned at the time of randomization and the identification number will be retained throughout the study. No personal identifying information will be included on the case report forms.

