**Table 5 – Intra-Procedure Guidelines**

Parameter	Description
-----------	-------------

Vascular access	Under sterile technique, the right and/or left femoral veins may be cannulated via Seldinger, or percutaneous approach. Other vascular access also may be obtained based upon physician judgment.
Reference catheter placement	Reference catheters (including 64-pole FIRMap catheter(s)) may be inserted and placed within the heart to record signals as clinically required at the discretion of the physician.
Access to left atrium	Access to the left atrium should be made according to the institution's standard practice.
Anticoagulation	Heparin should be administered per local protocol in order to achieve and maintain ACT > 300 prior to insertion of FIRMap catheter, if applicable. Heparin should be administered immediately following transeptal puncture in the case that ACT is not >300.
Catheter placement	Catheters may be inserted and used according to the institution's standard practice.
Source arrhythmia diagnosis	For FIRMap patients only: After obtaining at least 1 minute of continuous electrograms from the 64-pole FIRMap catheter either simultaneously or sequentially in the right and left atria, these electrogram data will be transferred to the RhythmView system. Right atrial mapping will initially be performed. If no right atrial rotor/source is detected or all right atrial rotors are eliminated, left atrial mapping will be performed. This will then produce FIRMap displays which will be interpreted by the operator to determine which locations have focal or rotor rhythms that could be sources of the AF.
3-D Electroanatomic Mapping	3-D electroanatomic maps may be created using CARTO (Biosense Webster, Johnson & Johnson) or Nav-X (St. Jude Medical) systems for documentation of anatomy and ablation lesion locations.
Induction of sustained AF	If the patient is not experiencing spontaneous, sustained AF (>5 min uninterrupted), induce sustained AF by atrial burst pacing from a catheter positioned within the CS or left atrial appendage until the atrial refractory period is reached or AF is induced with or without isoproterenol infusion.  IF AF CANNOT BE SUSTAINED, THE PATIENT DOES NOT MEET THE INCLUSION CRITERIA FOR THE PROTOCOL AND THE PATIENT WILL UNDERGO CONVENTIONAL AF ABLATION PER PHYSICIAN DISCRETION.

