Ablation data	For each ablation, the following data will be recorded: time, catheter size, lesion number, duration of application, average and maximum temperature.

FIRM-guided procedure	Under fluoroscopic guidance, a cardiac ablation catheter is passed to the location(s) identified as AF source rhythms (rotors or focal impulses). FIRM-guided ablation is performed at sites identified by the initial or repeated FIRMap. Such ablation typically consists of 3-5 minutes of ablation in the rotor core region followed by repeat mapping to confirm that the rotor has been eliminated. Following each FIRM guided site ablation, FIRMap is repeated and is followed by rotor ablation until all rotors are eliminated or AF terminates and remains noninducible. If AF terminates and is noninducible prior to repeat mapping, ablation of any identified and targeted rotor core region should be completed fully (e.g. ablation of the anatomic region with 3D electroanatomic guidance). In this FIRM-guided ablation arm, no PV isolation is performed. In case a rotor is located inside the PVs, focal ablation of the rotor (but no PVI) can be performed if the risk for PV stenosis is considered to be minimal as per discretion of the operator.
Conventional Ablation	Conventional ablation consists of isolation of all four pulmonary veins with confirmed entrance block assessed by a multipolar catheter.
Additional ablation for other arrhythmias (non-AF)	Additional ablation for other arrhythmias will be noted for atrial tachycardia (AT) and/or right cavo-tricuspid isthmus ablation in the event that the patient has documented AT/atrial flutter prior to or during the procedure.
ACT values	Activated Clotting Times (ACT) value is first measured prior to insertion of FIRMap catheter or trans-septal puncture, whichever comes first, to determine baseline value and then every 30 minutes post-heparinization until therapeutic and, subsequently, every 30 minutes during left-atrial access. (Heparin dosage should be adjusted to maintain ACT above 300 sec). The ACT will be monitored every 30 minutes following initial heparin delivery until the target value is achieved and subsequently checked at least every thirty minutes during the procedure.
Vascular access sheath removal	The vascular access sheaths will be removed according to the institutional standard.

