## 15 STATISTICAL CONSIDERATIONS

### 15.1 GENERAL ANALYSIS PRINCIPLES

All primary endpoint analyses will be conducted under the principle of "Intention-To-Treat" (ITT), where each subject randomized to a treatment group who has had a mapping and/or ablation catheter inserted shall be considered part of the ITT group. As a secondary exploratory analysis, a "Per Protocol" (PP) analysis may be performed with a subgroup of the ITT group who have no major protocol deviations reported.

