### 2.5.1 Handling of Screen Failures

Anticipated are two main types of screen failures. The first type will be screened by the clinical study site, and prior to randomization be classified as not eligible for inclusion into the study. The second type are subjects who fail entry criteria post-randomization, potentially while undergoing the procedure.

Screen failures will, at a minimum, have data collected reflecting completion of informed consent, demographic, and inclusion/exclusion criteria. If the screen failure occurred post-randomization, preparatory to undergoing the mapping/ablation procedure, these data will also be reflected in the clinical database.

Data on screen failures will be analyzed for any patterns observable as to demographic and inclusion/exclusion criteria, stratified by their randomization status and study site.

---

 Newcombe RG (1988) Interval estimation for the difference between independent proportions: comparison of eleven methods. *Statistics in Medicine* 17:873-890.

	FIRMAP AF Statistical Analysis Plan		Rev: 01	Effective: 05JAN2016
---	-------------------------------------	--	---------	----------------------

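### FIRM-assigned subjects switched to conventional ablation either dilute the by-arm safety comparison or may fall out of it: the plan does not say which, and plans no safety analysis by procedure performed

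*Protocol*

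**What the plan says.** **Order of events.** Protocol 7.4 places randomisation after baseline: "Randomization will occur if the subject is deemed eligible following screening baseline assessments and has signed the study informed consent form". Inclusion criterion 7, "Sustained AF (>5 min uninterrupted) during the electrophysiology procedure", can be checked only later, in the laboratory.

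**What happens on failure.** Protocol Table 5 states that a subject whose AF cannot be sustained does not meet the inclusion criteria, and adds "THE PATIENT WILL UNDERGO CONVENTIONAL AF ABLATION PER PHYSICIAN DISCRETION". This applies to both arms. For the FIRM arm it is a change of treatment, since the same table says of FIRM-guided ablation: "In this FIRM-guided ablation arm, no PV isolation is performed".

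**Who is in ITT.** Protocol 15.1 and SAP 2.1 agree: "each subject randomized to a treatment group who has had a mapping and/or ablation catheter inserted shall be considered part of the ITT group". Treatment received plays no part.

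**Safety denominator.** For acute safety, Protocol 15.2 D and SAP 2.2.3 use "the total count of subjects in that arm in the ITT group", compared by a chi-square test. Long-term safety (Protocol 15.2 C, SAP 2.2.4) is estimated by Kaplan-Meier per arm. It includes SAEs from repeat procedures, and its own section names no analysis set.

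**Screen failures.** SAP 2.5.1 expects two kinds: "The second type are subjects who fail entry criteria post-randomization, potentially while undergoing the procedure". On their data it says: "Screen failures will, at a minimum, have data collected reflecting completion of informed consent, demographic, and inclusion/exclusion criteria". For those who fail after randomisation, procedural data also enter the database. The analysis planned for them is a search for patterns in demographics and eligibility.

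**Other analysis sets.** The only one is an optional, exploratory per-protocol subset. SAP tables 3.1.5 to 3.1.7 present adverse events by treatment group.

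**The concern.** The protocol itself creates a group assigned to FIRM but ablated conventionally. The switch runs one way: a PVI-assigned subject without sustained AF still has conventional ablation, whereas a FIRM-assigned one leaves FIRM. Two rules then bear on the same people and are not reconciled.

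- Under the ITT wording, complications of their conventional ablation count as FIRM events. The FIRM arm becomes a mixture, and its SAE rate moves towards that of the comparator.
- Under the screen-failure wording they may be removed after randomisation. The minimum data named for them do not include adverse events, so their SAEs could be missing from both arms.

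Safety is part of the primary objective (Protocol 4, SAP 1.1.2), and SAP 1.2.1 lists acute and long-term safety under primary outcomes, although the Protocol makes them secondary. Both hypotheses are tests of equality, so attenuation pushes the result towards no difference detected. For harm, that is not the cautious direction.

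**Working it through.** **1. The plan's own figure.** The only sample-size calculation concerns effectiveness (Protocol 15.3, SAP 2.4): proportions 0.50 and 0.55, margin 0.15, one-sided 95% limit, 80% power.

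n per arm = (1.645 + 0.842)² × (0.50×0.50 + 0.55×0.45) / (0.05 + 0.15)² = 6.18 × 0.4975 / 0.04 ≈ 77.

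Exact enumeration of the Newcombe-Wilson limit at 77 per arm gives power 0.806. Adding the stated 16 gives 154 + 16 = 170, or 85 per arm. The figure reproduces. It does not concern safety, for which the documents give no SAE rates and no power.

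**2. Does a switched subject meet the ITT definition?** Yes on the words: the subject is randomised, and conventional ablation needs an ablation catheter in the heart. SAP 2.5.1 does not say whether its label overrides this.

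**3. If they stay in ITT.** Let f be the share of the FIRM arm switched, rF the SAE rate with FIRM-guided ablation and rC the rate with conventional ablation. Assume switched subjects have rate rC. Then:

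- by-arm FIRM rate = (1-f) × rF + f × rC
- by-arm difference = (1-f) × (rF - rC)

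None of f, rF and rC is in the documents. The table uses assumed values, in both directions of effect, with power of the two-sided 5% chi-square test at 85 per arm by exact enumeration.

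| Assumed rF / rC | f | By-arm FIRM rate | By-arm difference (points) | Power |
|---|---|---|---|---|
| 15% / 4% | 0 | 15.0% | 11.0 | 71.6% |
| | 10% | 13.9% | 9.9 | 64.0% |
| | 20% | 12.8% | 8.8 | 55.6% |
| | 30% | 11.7% | 7.7 | 46.5% |
| 10% / 4% | 0 | 10.0% | 6.0 | 32.2% |
| | 10% | 9.4% | 5.4 | 27.4% |
| | 20% | 8.8% | 4.8 | 22.9% |
| | 30% | 8.2% | 4.2 | 18.7% |
| 2% / 10% | 0 | 2.0% | -8.0 | 60.2% |
| | 10% | 2.8% | -7.2 | 47.6% |
| | 20% | 3.6% | -6.4 | 36.8% |
| | 30% | 4.4% | -5.6 | 28.0% |

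**4. How many events are involved?** Expected conventional-ablation SAEs counted in FIRM = 85 × f × rC. At rC = 4% and f = 10, 20, 30%: 0.34, 0.68, 1.02. At rC = 10%: 0.85, 1.70, 2.55.

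**5. If they are removed instead.** The dilution in step 3 does not arise. Up to 85 × f FIRM-assigned subjects (8.5, 17, 25.5 at the same f), and PVI-assigned subjects who fail the same check, leave a randomised comparison after allocation. Whether their SAEs are tabulated anywhere is not stated.

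**The case against.** A reader might infer that PVI complications are certainly booked to FIRM and that the reported FIRM rate is therefore wrong. The documents do not go that far, for these reasons.

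- **Membership of ITT is open.** Table 5 says these subjects fail the inclusion criteria, Protocol 7.3 counts a subject as enrolled only once all criteria are met, and SAP 2.5.1 calls them screen failures. Dropping them is a tenable reading, and then there is no dilution. This stands, and it is why the point has two branches.
- **The substitute is not necessarily PVI.** It is left to the physician. A FIRM-assigned subject may also have had the FIRMap catheter placed before the switch, and harm from that properly belongs to the FIRM strategy. The (1-f) formula is therefore an approximation. This stands.
- **Few events are involved.** At a 4% rate, about 0.3 to 1.0 SAEs are misplaced, and the safety comparison is weakly powered in the 10% v 4% example even with no switching (32.2%). This stands as a limit on size.
- **There is partial cover.** The per-protocol subset would drop these subjects if their failure is logged as a major deviation (Protocol 12.4), and listings 3.2.2 to 3.2.4 let a reader trace events by subject. But that subset is optional, and it removes the SAEs rather than showing them against the procedure performed.
- **SAEs may well be collected.** Protocol 10 calls for all adverse events during the study to be recorded, and the SAP's screen-failure data set is only a minimum. Uncounted SAEs are thus a risk, not a stated rule.
- **ITT may not govern long-term safety.** Protocol 15.1 states it for primary endpoint analyses, and 15.2 C names no set. The literal argument is firm only for acute safety.

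Finally, the by-arm comparison is not an error. It is the randomised one and describes the strategy of intending FIRM.

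**Conclusion.** The concern holds in conditional form. On the literal ITT wording, FIRM-assigned subjects ablated conventionally remain in the FIRM acute-safety denominator, and the by-arm SAE difference is (1-f) of its true size if they carry the conventional-ablation risk. On the screen-failure wording they may leave, and their SAEs may be counted in neither arm. Either way the plan offers no presentation of safety by procedure performed.

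The direction of the dilution follows from the arithmetic; its size cannot be fixed from the documents. At an assumed f of 10 to 30%, it is 10 to 30% of the true difference. The rates and powers above illustrate assumed values and are not estimates for this trial. The point warrants a change to the plan, but it does not show that the planned safety result would be invalid.

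**What to change.** 1. **Reconcile the ITT rule (Protocol 15.1, SAP 2.1) with SAP 2.5.1.** State that every randomised subject with a catheter inserted stays in the by-arm safety analysis, and that SAEs are collected for all of them.
2. **Add a supportive analysis in Protocol 15.2 C and D and SAP 2.2.3 and 2.2.4.** Keep the randomised-arm analysis. Beside it, show safety by index procedure actually performed: FIRM-guided ablation; conventional ablation as assigned; and, in a separate column only, FIRM-assigned subjects switched to conventional ablation. For that column give the number switched, their SAEs, and whether each arose before or after the switch.
3. **Produce SAP tables 3.1.5 to 3.1.7 both ways.** For long-term safety, show SAEs from repeat procedures separately, since the index procedure does not describe them.

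None of this alters how subjects are treated. The cost is SAP and Protocol wording, a second version of three tables, and the timing of each SAE relative to the switch. The procedure performed should be available from the index-procedure outputs already planned (table 3.1.2, listing 3.2.2). The drawback is that the by-procedure groups are not randomised, and subjects whose AF cannot be sustained may differ from the rest. The addition should be labelled supportive and should not replace the by-arm result.

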## 4 **STUDY OBJECTIVES**

The primary objective is to compare the safety and effectiveness of FIRM-guided ablation procedures with conventional RF based pulmonary vein isolation ablation procedure for the treatment of paroxysmal atrial fibrillation (AF) for subjects without prior AF catheter ablation.

The secondary objective is to evaluate the treatment time and quality of life outcomes.

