### 15.2 STUDY ENDPOINTS

#### A. Long-Term Effectiveness (Primary effectiveness endpoint)

The primary effectiveness endpoint is single-procedure freedom from AF/AT recurrence from 3-12 months after the index AF ablation procedure (with 90-day blanking period).

The hypothesis to be tested is the recurrence rate for FIRM-guided AF ablation is not inferior to that experienced by the conventional AF ablation arm.

The statistical hypothesis for this endpoint is operationalized as follows:

$$H_0: \delta > .15$$

$$H_A: \delta < .15$$

$$\alpha = .05 \text{ (two-tailed)}$$

Where:

$$\delta = p_C - p_F$$

$p_C$  = Proportion free from AF recurrence at twelve (12) months post index ablation procedure for the conventional AF ablation arm (.50)

$p_F$  = Proportion free from AF recurrence at twelve (12) months post index ablation procedure for the FIRM-guided AF ablation arm (.55)

The non-inferiority margin for this hypothesis is 15% (.15). If the lower limit of the two-sided 95% confidence interval calculated for the difference in proportions ( $\delta$ ) is less than .15, the null hypothesis will be rejected and evidence in favor of the alternative (FIRM-guided ablation for atrial fibrillation is not inferior to conventional ablation for atrial fibrillation) affirmed.

This non-inferiority margin was chosen based on that used in the FreezeAF and VGLB trials.

 Luik, Armin MD, et. al. (2010). Rationale and design of the FreezeAF trial: A randomized controlled noninferiority trial comparing isolation of the pulmonary veins with the cryoballoon catheter versus open irrigated radiofrequency ablation in patients with paroxysmal atrial fibrillation. American Heart Journal. 159(4):555-560.

The proportion of successes in each treatment arm shall be estimated using Kaplan-Meier survival estimation.

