#### 15.3 POWER AND SAMPLE SIZE ESTIMATION

Since the primary objective of this study relates to the long-term effectiveness of FIRM-guided ablation versus conventional ablation for atrial fibrillation (AF), power and sample size estimates have been calculated relative to that endpoint only. We anticipate enrolling 77 subjects in each treatment arm, plus an additional 8 subjects per arm to account for possible drop-outs / lost to follow-ups, for a total of 170 subjects (in approximately 20 sites).

Description	Assumptions
FIRM Group Freedom from recurrence of AF at 3 months	.55
CONVENTIONAL Group Freedom from recurrence of AF at 3 months	.50
Probability of Type I error ( $\alpha$ ) (two-sided test)	.05
Minimum Total Sample Size (includes 10% adjustment for drop-outs and losses to follow-up)	170 (85 per group)

With 77 subjects in each group, the lower limit of the observed one-sided 95.0% confidence interval will be expected to exceed -0.150 with 80% power when the Standard proportion,  $p_c$ , is 0.500 and the Test expected proportion,  $p_F$ , is 0.550; results are based on 1000 simulations using the Newcombe-Wilson score method to construct the confidence interval. In order to account for potential drop-outs and losses to follow-up, an additional 10% (16) will be added to the total sample size, for a final sample size of 170 (85 per group).

This power and sample size calculation was performed using NQuery 7.0 on the Microsoft Windows 10 operating system.

---

 Newcombe RG (1988) Interval estimation for the difference between independent proportions: comparison of eleven methods. *Statistics in Medicine* 17:873-890.

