## 1.2 Study Outcomes

### 1.2.1 Primary Outcomes

#### 1.2.1.1 Acute Safety

Freedom from procedure-related serious adverse events within 7 days of the procedure.

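### Both safety endpoints test equality with no interval for the difference, so a non-significant result cannot support a conclusion of acceptable safety

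*Protocol*

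**What the plan says.** **Objective.** Protocol section 4 states: "The primary objective is to compare the safety and effectiveness of FIRM-guided ablation procedures with conventional RF based pulmonary vein isolation ablation procedure". SAP 1.1.2 also puts safety in the primary objective.

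**Acute safety** (Protocol 15.2 D, SAP 2.2.3). The endpoint is "freedom from serious adverse events related to the procedure within seven (7) days of the index procedure". The null hypothesis is equal proportions in the two arms, two-sided at .05. The analysis is given as "The analysis to be performed for this endpoint will be a Chi-square test of Independence".

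**Long-term safety** (Protocol 15.2 C, SAP 2.2.4). The same equality hypothesis applies at one year, and repeat procedures are counted. The only method given is "The proportion of successes in each treatment arm shall be estimated using Kaplan-Meier survival estimation". No test or other comparison between the arms is named.

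**Effectiveness, for contrast** (Protocol 15.2 A, SAP 2.2.1). Here there is a non-inferiority hypothesis, a margin of .15 and a two-sided 95% confidence interval for the difference.

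**Size** (Protocol 15.3, SAP 2.4). Both sections say that "power and sample size estimates have been calculated relative to that endpoint only", meaning long-term effectiveness.

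**Rank of safety.** The Protocol lists both safety endpoints as secondary (section 6.2 and the headings of 15.2 C and D), and 15.3 describes the primary objective in terms of effectiveness. The SAP puts both under Primary Outcomes (1.2.1.1 and 1.2.1.2) and calls long-term safety primary in 2.5 and 2.6.

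**The concern.** A non-inferiority claim on effectiveness has to be weighed against safety. The useful question for safety is how large an excess of procedure-related SAEs with FIRM the data can rule out. A test of equality does not answer it: failure to reject may mean similar rates, or too few events to tell. An interval separates the two.

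The plan supplies an interval and a margin for effectiveness but neither for safety, and the sample size was not chosen with safety in mind. If the acute test is not significant, the planned comparison leaves the reader without a stated limit on the possible harm. For long-term safety, the hypothesis is written down but nothing says how it would be tested or the difference estimated.

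**Working it through.** **1. The plan's own figure.** Inputs from Protocol 15.3: success .50 (conventional) and .55 (FIRM), margin .15, one-sided 95% limit, 80% power.

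n per arm = (1.645 + 0.842)² × (.50×.50 + .55×.45) / (.15 + .05)² = 6.183 × 0.4975 / 0.04 = 76.9, so 77.

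Then 2 × 77 × 1.10 = 169.4, so 170 in total or 85 per arm. This reproduces the plan. No safety quantity enters it.

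**2. Power of the acute safety test.** The documents give no SAE rate, so control rates of 1% to 10% are my assumption. For arms of n = 85 with x and y events, the uncorrected chi-square statistic reduces to 2n(x − y)² / [(x + y)(2n − x − y)]. I summed the binomial probabilities of all outcomes where it exceeds 3.84.

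| Control rate | FIRM rate | Power | Missed |
|---|---|---|---|
| 1% | 2% | 4% | 96% |
| 2% | 4% | 10% | 90% |
| 3% | 6% | 13% | 87% |
| 5% | 10% | 22.5% | 77.5% |
| 8% | 16% | 36% | 64% |
| 10% | 20% | 45% | 55% |
| 5% | 15% | 60% | 40% |
| 5% | 20% | 87% | 13% |

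Power of about 80% needs roughly 15% against 3%, or 18.5% against 5%. Conversely, 80% power for 10% against 5% would need about 435 per arm.

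**3. What an interval would show.** The Newcombe-Wilson limits use the Wilson limits (l, u) of each arm's rate, with d = p_F − p_C:

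- lower = d − √[(p_F − l_F)² + (u_C − p_C)²]
- upper = d + √[(u_F − p_F)² + (p_C − l_C)²]

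Example with 11 FIRM and 4 PVI events out of 85 each:

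- FIRM: 12.9%, Wilson limits 7.4% to 21.7%. PVI: 4.7%, Wilson limits 1.8% to 11.5%.
- d = 8.2 points.
- Lower = .0824 − √(.0556² + .0678²) = −.005. Upper = .0824 + √(.0876² + .0286²) = .175.
- Chi-square = 170 × 7² / (15 × 155) = 3.58, p = 0.058.

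| Events FIRM / PVI | Difference (points) | 95% interval (points) | Chi-square p |
|---|---|---|---|
| 2 / 2 | 0.0 | −6.1 to +6.1 | 1.00 |
| 4 / 4 | 0.0 | −7.4 to +7.4 | 1.00 |
| 8 / 4 | +4.7 | −3.5 to +13.3 | 0.23 |
| 11 / 4 | +8.2 | −0.5 to +17.5 | 0.058 |

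All four rows are non-significant, but the excess not excluded runs from about 6 to about 17 points.

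**4. Zero events.** The chance that an arm of 85 has no event is .99^85 = 43% at a true rate of 1%, and .98^85 = 18% at 2%. In that case the plain Greenwood variance of the Kaplan-Meier estimate is zero, so the long-term interval needs another method.

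**The case against.** **Safety is secondary and openly unpowered.** This is partly right. The Protocol ranks it so, and 15.3 is candid about what was sized. But section 4 of the Protocol and the SAP give it a higher place, and low power is itself the reason to report an interval.

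**The safety data will be visible anyway.** This stands as far as it goes. Per-arm proportions, a Kaplan-Meier safety figure, adverse event tables that include acute SAEs, and listings are planned (SAP section 3). Missing acute data are shown two ways (SAP 2.5), and a Data Monitoring Committee reviews safety. Anyone could compute an acute interval from the counts. What is absent is a pre-specified one. SAP 2.6 does not fill the gap: its Cochran-Mantel-Haenszel and Cox analyses are aimed at centre effects, and no treatment interval is mentioned.

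**Stronger readings.** A reader might infer that a non-significant result is almost certain, that it is the only safety result available, or that it says nothing. The documents do not support these. The chance of non-significance depends on an SAE rate they do not give. A tripling from 5% would be detected 60% of the time and a quadrupling 87%. If the arms are truly equal, non-significance in about 95% of trials is what any valid 5% test gives, and is no defect. A reader might also infer that the sponsor plans to report p > .05 as comparable safety; neither document says so.

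**Conclusion.** The point holds. Safety belongs to the stated primary objective, but it is framed only as a null hypothesis of equality. No interval is planned for either safety difference, and no between-arm comparison is named for long-term safety. A non-significant result could not support a conclusion of acceptable safety.

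The miss rate for a true doubling is about 55% to 96%. It rests on assumed control SAE rates of 10% down to 1%, on 85 analysed subjects per arm and on the uncorrected chi-square test. Very large excesses would usually be found. The case for an interval does not depend on any one of these rates. The conflict over the rank of safety affects how much weight the point carries and needs its own correction. This change should be made; the design and sample size need not change.

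**What to change.** In Protocol 15.2 C and D and SAP 2.2.3 and 2.2.4:

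1. **Acute safety.** Make the main result the SAE risk difference, FIRM minus PVI, with a two-sided 95% Newcombe-Wilson interval, the method already used for sizing. Keep the chi-square p-value as descriptive.
2. **Long-term safety.** Make the main result the one-year Kaplan-Meier difference with a 95% interval, and name this as the between-arm comparison. Specify a method that stays valid with few or no events, such as per-arm Wilson-type limits combined in the Newcombe manner, with a stated rule for an arm without events. Per-arm log-log limits would serve with few events but are undefined with none. Plain Greenwood limits should not be used.
3. **Interpretation.** State that p > .05 will not be reported as comparable safety, and that the conclusion will quote the largest excess SAE risk not excluded by the interval.
4. **Rank.** Reconcile the status of safety across Protocol sections 4, 6.2, 15.2 and 15.3 and SAP 1.1.2, 1.2.1, 2.4, 2.5 and 2.6.

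The cost is wording and two intervals, with no extra subjects or data. The one downside for the sponsor is a less favourable safety statement.
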